## 6 STATISTICAL ANALYSES

## 6.1 General Statistical Considerations

## 6.1.1 Software

Version 9.2 or higher of SAS® statistical software package or other validated statistical software will be used to provide all summaries, listings, graphs, and statistical analyses.

## 6.1.2 Descriptive Statistics

Continuous data will be summarized using descriptive statistics: n, mean, standard deviation or standard error, median, minimum and maximum. The decision to use either standard deviation

or standard error will be based upon the objective of the presentation: standard deviation will be used when the interest is the natural variability of the data; standard error will be used when comparing two or more means. Continuous variables that are recorded using approximate values (e.g., < or >) will be replaced by the closest exact value for the calculation of summary statistics.

Categorical variables will be summarized using frequency counts and percentages. When count data are presented, the percentage for zero counts may be suppressed in order to draw attention to the non-zero counts.

For ordinal-scaled variables, a combination of the above may be employed as appropriate: frequency and percentage of observations within a category and means and standard deviations of the scores of the categories.

For categorical and ordinal variables, percentages will be calculated based on non-missing data.

## 6.1.3 P-values

Unless otherwise specified statistical analyses will be performed using a two-sided hypothesis test at the overall 5% level of significance. P-values will be rounded to three decimal places. If a p-value is less than 0.001 it will be reported as "< 0.001". If a p-value is greater than 0.999 it will be reported as "> 0.999". No adjustments for multiplicity are planned.

## 6.1.4 Duration Variables

Study Day 1 is the day of study device deployment (index procedure).

Study day is calculated relative to day 1 and will appear in the listings where applicable.

Study day after the index procedure will be calculated as:

Study Day = (Date of Event – Date of Study Device Deployment +1).

Study day prior to the index procedure will be calculated as:

Study Day = (Date of Event – Date of Study Device Deployment).

Duration variables will be calculated using the general formula:

[(end date – start date+1)]

## 6.1.5 Kaplan-Meier Analysis

For time to event endpoints analyzed with a Kaplan-Meier method, analysis time points will be presented at 30 and 180 days. Unless otherwise specified, if a subject is event-free, their date of censoring will be considered as the date of last contact in the study. For Kaplan-Meier estimates presented with the corresponding 95% log-log confidence interval  $(L_{\hat{s}}, U_{\hat{s}})$ , Greenwood's estimate of the standard error will be used. The Kaplan-Meier estimate of the event rate,  $\hat{F}$ , may be computed as  $1 - \hat{S}$  and the corresponding 95% log-log confidence interval is as follows:

$$L_{\hat{F}} = 1 - U_{\hat{S}} \\ U_{\hat{F}} = 1 - L_{\hat{S}}.$$

## 6.1.6 Missing Data

Unless otherwise specified, techniques will not be used to impute missing data. If a subject (or lesion) is missing a data point for any reason, that subject (or lesion) will not be included in that portion of the analysis. The number of data values available for each analysis will be reported so that the reader can assess the potential impact of missing data.

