## 6.3.3 Change in Ankle-Brachial Index (ABI)

Change in ankle-brachial index (ABI) from pre-procedure (i.e., baseline) to 30 days and 6 months.

The endpoint will be summarized for the mITT set. Within-subject changes will be calculated as visit value minus baseline value such that a negative change reflects a deterioration and a positive change signifies an improvement. Summaries of improved/same/worsened will be provided along with continuous summaries.

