## 6.3.4 Change in Rutherford Classification

Change in Rutherford classification from pre-procedure (i.e., baseline) to 30 days and 6 months.

The endpoint will be summarized for the mITT set. Within-subject changes will be calculated as visit value minus baseline value such that a negative change reflects an improvement and a positive change signifies a deterioration. Summaries of improved/same/worsened will be provided alongside the ordinal summaries.

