## 6.3.8 Primary Patency, Primary Assisted Patency and Secondary Patency

Primary patency, primary assisted patency and secondary patency will be derived on a *per-lesion* level.

Primary patency is defined as the absence of target lesion restenosis evaluated by duplex ultrasound (i.e., peak systolic velocity ratio  $[PSVR] \le 2.5$ ) and freedom from clinically-driven target lesion revascularization. The primary patency success must meet success criteria for the both components of patency. If the lesion fails either component of the patency endpoint, the lesion will be considered a failure for the efficacy endpoint.

Primary assisted patency is defined as patency of the target lesion following endovascular reintervention at the target vessel site in case of symptomatic restenosis. This is a cumulative

patency rate including patent target lesion post re-intervention for restenosis at the given followup timepoint.

Secondary patency reports patency of the target lesion after treatment of a (re)occlusion of the index lesion. This is a cumulative patency rate, including re-intervention (restenosis or re-occlusion) at the given follow-up timepoint.

A Kaplan-Meier (KM) survival analysis as described in Section 6.1.5 will be used to estimate the patency rates including primary, primary asissted and secondary. The patency rates will be presented as the KM estimate of freedom from loss of patency at 30 days and 180 days post-procedure. The survival curves, the KM estimate, and the 95% confidence interval will be presented. Lesions will be censored at the day of last subject follow-up for the following senarios:

- Have 6 months follow-up but no analyzable duplex ultrasound data, and no clinicallydriven TLR
- Have no 6 months follow up but also have no event of interst.

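### Deaths, and amputations that prevent measurement, leave the 6-month improvement percentages; the patency analysis censors amputated limbs and has no rule for a duplex without flow

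*SAP*

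**What the plan says.** SAP 6.1.6 imputes nothing unless stated otherwise: "If a subject (or lesion) is missing a data point for any reason, that subject (or lesion) will not be included in that portion". SAP 6.1.2 sets the denominator: "For categorical and ordinal variables, percentages will be calculated based on non-missing data".

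SAP 6.3.3 to 6.3.5 summarise change in ABI, Rutherford class and VascuQoL at 30 days and 6 months in the mITT set. Each adds a three-way split. For ABI, "Summaries of improved/same/worsened will be provided along with continuous summaries"; for Rutherford class, "Summaries of improved/same/worsened will be provided alongside the ordinal summaries"; VascuQoL has the same. None of the three sections has a rule for death or amputation.

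SAP 6.3.8 defines primary patency per lesion as "absence of target lesion restenosis evaluated by duplex ultrasound" (PSVR of 2.5 or less) together with freedom from clinically driven TLR. A lesion that fails either component is a failure. Rates come from Kaplan-Meier estimates. Two kinds of lesion are censored at the subject's last follow-up. The first is described as "Have 6 months follow-up but no analyzable duplex ultrasound data" and no clinically driven TLR. The second has neither a 6-month follow-up nor an event. Amputation is not named as loss of patency. Occlusion appears only under secondary patency.

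**The concern.** Death and loss of the target limb are outcomes, and bad ones. Treating them as absent data takes them out of the denominator, and the share improving can only rise or stay the same, because none of these subjects could have been counted as improved. The trial has one arm, so no control group carries the same distortion.

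Timing adds to this. Cardiovascular death and unplanned major amputation through 30 days count against the primary safety endpoint (Protocol 5.2). The same events between 30 days and 6 months count against no effectiveness summary and appear only in the adverse-event and disposition tables. Subjects with rest pain or ischemic wounds are eligible (Protocol 6.1.1), and death and amputation are listed risks (Protocol 7.2).

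For patency, Kaplan-Meier censoring assumes that a censored lesion would have had the same later course as the lesions still under observation. That is hard to defend for a limb that has been amputated.

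**Working it through.** The plan gives no figure on this point, so there is none to reproduce. It also gives no 6-month rate of death, amputation, improvement or patency. The sizes below are illustrations.

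**Step 1. Who leaves which summary.**
- *Death before the visit:* no value for ABI, Rutherford class or VascuQoL, so the subject leaves all three percentages.
- *Target-limb amputation:* Protocol 5.2 starts at the transmetatarsal level, so the ankle may remain. The subject leaves only those summaries whose measure can no longer be made.
- *Patency after amputation:* with no earlier restenosis or TLR and no readable 6-month duplex, one of the two censoring rules in SAP 6.3.8 applies.
- *No flow on duplex:* there is no velocity ratio to compare with 2.5. The SAP does not say whether such a study is analysable, so the class is undefined.

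**Step 2. Improvement percentages.** Assumptions: N = 112 (the planned total), about 80% improved and 5% worsened among observed subjects (rounded to whole subjects), m subjects dead or unmeasurable, and nobody else missing.

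Plan: improved / (N − m). All mITT: improved / N. For worsening, the all-mITT column takes the extreme case in which every such subject counts as worsened: (worsened + m) / N.

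| m | Improved, plan | Improved, all mITT | Worsened, plan | Worsened, all mITT |
|---|---|---|---|---|
| 2 | 88/110 = 80.0% | 88/112 = 78.6% | 6/110 = 5.5% | 8/112 = 7.1% |
| 6 | 85/106 = 80.2% | 85/112 = 75.9% | 5/106 = 4.7% | 11/112 = 9.8% |
| 10 | 82/102 = 80.4% | 82/112 = 73.2% | 5/102 = 4.9% | 15/112 = 13.4% |

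**Step 3. Patency.** Assumptions: 112 lesions (one per subject), 15 observed failures at day 180, and k further lesions in amputated limbs or with no flow.

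Censored at day 180, they are still at risk when the failures occur: 1 − 15/112 = 86.6% for any k. Censored at day 90: 1 − 15/(112 − k). Counted as loss of patency: (112 − 15 − k)/112.

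| k | Censored day 180 | Censored day 90 | Loss of patency |
|---|---|---|---|
| 2 | 86.6% | 1 − 15/110 = 86.4% | 95/112 = 84.8% |
| 6 | 86.6% | 1 − 15/106 = 85.8% | 91/112 = 81.25% |
| 10 | 86.6% | 1 − 15/102 = 85.3% | 87/112 = 77.7% |

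The gap applies to amputated limbs as the SAP is written. It applies to no-flow lesions only if they are read as not analysable.

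**Step 4. Reach.** Technical success is a procedural endpoint. The 30-day safety endpoint has its own denominator and dropout rule (SAP 6.2.2). Neither uses these summaries, so the sample size and power calculations do not change.

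**The case against.** The best defence is that change among observed subjects is a legitimate descriptive summary, and that no secondary endpoint is tested (SAP 6.3). The SAP is also open about losses: "The number of data values available for each analysis will be reported so that the reader can assess the potential impact of missing data". SAP 6.5.2 tabulates discontinuations by reason and SAP 6.4 lists every adverse event by subject. Counting all deaths as not improved brings in deaths unrelated to the limb. Numbers may be small, because eligibility stops at Rutherford 5 and excludes a life expectancy under 12 months.

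Most of this stands, and it limits the weight of the point. It does not remove it. An available count does not separate a death from a missed visit, and tables elsewhere do not correct the percentage that will be quoted.

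A reader might infer more than the documents support:
- *That an occluded lesion is censored as patent.* The SAP does not say so. Success requires both components, and SAP 6.1.9 contrasts diagnostic with non-diagnostic duplex. A scan that documents no flow could therefore be diagnostic and a failure. SAP 6.1.9 also lets in-window angiography stand in when duplex is unavailable, although follow-up angiography is done only for symptoms requiring intervention (Protocol 6.7 and 6.8). What can be said is that the rule is missing.
- *That every amputee leaves all three summaries.* A living amputee can complete a questionnaire, a Rutherford class may still be recorded, and ABI may survive a transmetatarsal amputation.
- *That only open limbs are summarised.* Occlusion does not stop ABI, Rutherford class or VascuQoL from being recorded.
- *That a censored lesion counts as patent throughout.* It counts as event-free only up to its censoring date.

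**Conclusion.** The point holds in a limited form. By stated rule, deaths and amputations that prevent measurement leave the improved/same/worsened denominators, and an amputated limb without an earlier patency event is censored as if that were uninformative. By omission, a duplex without flow has no defined class. The 6-month descriptive figures are biased upward. Under the assumed inputs, with 2 to 10 such subjects, the excess in the improved share runs from 80.0 − 78.6 = 1.4 to 80.4 − 73.2 = 7.2 percentage points. With 2 to 10 such lesions, the patency excess runs from about 1.6 to 8.9 points across the two censoring dates, and the part due to no-flow lesions depends on the unsettled reading. The real size rests on event counts the documents do not give. The primary endpoints and the trial's success criterion are untouched, so this is a change the sponsor should make rather than a flaw in the main conclusion.

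**What to change.** In SAP 6.3.3 to 6.3.5, add a fourth category to improved/same/worsened: death, or major target-limb amputation preventing measurement, before the visit. Keep it in the denominator as not improved. Show these percentages beside the observed-case ones, and show deaths within the category so that limb-unrelated deaths are visible. Leave subjects who merely missed the visit as they are now, and leave continuous summaries on observed values.

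In SAP 6.3.8, state that occlusion documented on duplex (no flow) is loss of patency. Where a lesion would otherwise be censored after major target-limb amputation, count it as loss of patency, or report patency both ways.

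The cost is a few SAP sentences and one table row, from data already collected, settled before database lock. The downside is slightly lower percentages and some limb-unrelated deaths counted as not improved.

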## 6.1.7 Partial Dates

In the case of partial dates, the dates of the event will be imputed. Imputation of partial dates is subject to the condition that the imputed date occurs on or after the procedure date and on or before the subject's last contact date. In the case of adverse events and other data fields with partial start and stop dates, the imputed dates are subject to the additional condition that the start date must occur on or before the stop date.

	Valid Portion	Missing Portion	Imputed Value for Missing Portion 	
	Month,	Day	Set day to 15th day of the known month and	
	Year		year	
Start Date	Year	Day, Month	Set date to June 30th of the known year	
	None	Day, Month,	Date of procedure	
		Year		
	Month,	Day	Set day to 15 th day of the known month and	
	Year		year	
Stop Date 	Year	Day, Month	Set date to June 30th of the known year	
-	None	Day, Month,	None	
		Year		
 Imputed date	must occur on or	after the procedure d	late. For adverse events and concomitant medications, the	
start date mus	t occur on or befo	ore the stop date.		
 Date of death will be imputed nor the imputation rules for a stort date				

Date of death will be imputed per the imputation rules for a start date.

## 6.1.8 Visit Windows and Visit Definitions

For the purposes of analysis, a visit will be considered in-window if it occurs within the intervals detailed below as specified in the protocol, and out of window otherwise.

Study Visit	Window	Target
Baseline	Any CRF entered in the	Any CRF entered in the
	Baseline visit	Baseline visit
	Labs within 30 days	
Discharge	Any follow-up CRF entered	Any follow-up CRF entered
	in the Discharge visit	in the Discharge visit
1 Month	23-37 Days	30 Days
6 Month	166-194 Days	180 Days

Baseline is defined as the last measurement for the outcome of interest obtained before the exposure to the study device.

## 6.1.9 Duplex Ultrasound Assessments

In the case that multiple duplex assessments (e.g., a duplex ultrasound was non-diagnostic, requiring a repeat ultrasound) of the target lesion are performed within the visit window, the first diagnostic duplex assessment will be used as the basis for analysis. In the cases where angiography data are available within a protocol-defined window, and duplex ultrasound assessment is not available, angiographic data will be used to determine the patency.

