6.6 POST PROCEDURE TO DISCHARGE

The following assessments will be performed within 12-24 hours post procedure or prior to hospital discharge, whichever occurs first:

- Physical Exam and Vital Signs
- Adverse Events assessment

6.7 30 DAYS FOLLOW-UP (± 7 DAYS)

Subjects will return for a follow-up visit at 30 days and the following assessments will be performed:

- Physical Exam and Vital Signs
- Rutherford Classification
- ABI and/or TBI
- Duplex ultrasound of treated lesion per Vascular Ultrasound Core Laboratory protocol
- Angiogram performed only if clinical symptoms requiring intervention during follow-up for TVR or TLR
- VascuQoL Questionnaire
- Adverse Events assessment

6.8 6 MONTHS FOLLOW-UP (± 14 DAYS)

Subjects will return for a follow-up visit at 6 months and the following assessments will be performed:

- Physical Exam and Vital Signs
- Rutherford Classification
- ABI and/or TBI
- Duplex ultrasound of treated lesion per Vascular Ultrasound Core Laboratory protocol
- Angiogram performed only if clinical symptoms requiring intervention during follow-up for TVR or TLR
- VascuQoL Questionnaire
- Adverse Events assessment

Table 6-1: Schedule of Events

Assessment	Screening / Baseline	Procedure	Discharge	30 Days (±7 days)	6 months (±14 days)
Informed Consent	Х				
Medical History	Х				
Physical Exam	Х		Х	Х	Х
Laboratory Assessments	Х	Х			

Urine Pregnancy Test if female	Х				
Rutherford Classification	Х			Х	Х
ABI	Х			Х	Х
VascuQoL Questionnaire	Х			Х	Х
Angiography	X ^a	Х		Xb	X ^b
Duplex Ultrasound	X ^c			Х	Х
Medications	Х		Х	Х	Х
Adverse Events	Х	Х	Х	Х	Х

^a Baseline angiography will be performed at the beginning of index procedure.

^b Angiography will be performed at the follow-up visits for verification of restenosis of the treated lesion or vessel site(s) only if the subject has clinical symptoms requiring intervention.

^c if available

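### SAP 6.1.9 and SAP 6.3.8 disagree on a lesion with an in-window angiogram, no usable duplex and no clinically driven TLR, and the angiographic fallback has no restenosis criterion

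*SAP*

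**What the plan says.** SAP 6.1.9 gives duplex ultrasound precedence and adds a fallback: if there is angiography inside a protocol-defined window "and duplex ultrasound assessment is not available, angiographic data will be used to determine the patency". It gives no stenosis cut, no reader and no rule on which image counts.

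SAP 6.3.8 derives patency per lesion. "Primary patency is defined as the absence of target lesion restenosis evaluated by duplex ultrasound", with a peak systolic velocity ratio (PSVR) of at most 2.5, "and freedom from clinically-driven target lesion revascularization". Failing either part is a loss: "If the lesion fails either component of the patency endpoint, the lesion will be considered a failure for the efficacy endpoint". Protocol 5.3 likewise gives only duplex and PSVR 2.5 for this endpoint, read by the Vascular Ultrasound Core Laboratory.

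The rates are Kaplan-Meier estimates at 30 and 180 days. "Lesions will be censored at the day of last subject follow-up" in two scenarios. The first covers lesions that "Have 6 months follow-up but no analyzable duplex ultrasound data" and no clinically driven TLR. Angiography is not mentioned.

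Protocol 6.7 and 6.8 restrict follow-up angiography: "Angiogram performed only if clinical symptoms requiring intervention during follow-up for TVR or TLR". SAP 6.3 makes all secondary endpoints descriptive and also reports them by product power type.

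**The concern.** Take a target lesion with an angiogram inside days 166-194, no usable duplex and no clinically driven TLR. Under SAP 6.1.9 the angiogram decides whether it is open. Under the first scenario of SAP 6.3.8 it is censored whatever the angiogram shows. Neither section refers to the other or says which prevails.

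The documents allow such lesions to arise. Angiography may be done for target vessel revascularization and show a restenosed target lesion that is not retreated. A subject may have up to three target lesions, with one retreated and another left alone. A TLR may not be adjudicated as clinically driven. Such lesions come from limbs with symptoms, so censoring them is unlikely to be neutral.

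At stake is the 6-month primary patency rate. If the censoring scenario is followed, an observed restenosis leaves the analysis as if its outcome were unknown. If SAP 6.1.9 is followed, someone must choose a stenosis cut at the programming stage, in an open single-arm trial where results can be seen.

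**Working it through.** The plan states no patency rate, precision or sample size for this endpoint, so there is no figure to reproduce. The check has two parts.

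**1. The rules side by side, for a lesion with 6-month follow-up**

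| Lesion | SAP 6.1.9 | SAP 6.3.8 |
|---|---|---|
| Analyzable duplex | Duplex decides | Duplex decides |
| No usable duplex, clinically driven TLR | Angiogram, if in window | Failure (second component) |
| No usable duplex, no clinically driven TLR, no angiogram | No rule | Censored |
| No usable duplex, no clinically driven TLR, in-window angiogram | Angiogram decides | Censored |

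Only the last row conflicts when the angiogram shows restenosis. The triggers also differ slightly: SAP 6.1.9 speaks of duplex that is not available, SAP 6.3.8 of duplex that is not analyzable. A non-diagnostic duplex plus an angiogram clearly meets only the second.

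**2. Size of the effect per lesion**

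From the documents:
- 6-month window of days 166-194, target day 180 (SAP 6.1.8); estimate at day 180 (SAP 6.3.8).
- 112 subjects, about 56 per device version (Protocol 4.2).
- Up to three target lesions each (Protocol 6.5.1), so 112 to 336 lesions.

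Assumed:
- About 11% of lesions have lost patency before day 166 (6 of 56, 12 of 112, 17 of 160).
- Last visits are uniform over days 166-194, with no other losses in the window.
- One to three lesions are affected. The documents give no number, and zero is equally consistent with them.

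Let n be the number of lesions and p the prior losses. At day 166 the estimate is (n - p)/n with n - p lesions at risk. After u further days the number at risk is (n - p)(1 - u/28). Recoding one lesion from censored to failed at that time lowers the estimate by

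[(n - p)/n] / [(n - p)(1 - u/28)] = 1 / [n(1 - u/28)].

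The prior losses cancel.

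- Angiogram uniform over days 166-180: the average is (2 ln 2)/n = 1.386/n.
- Angiogram uniform over the whole window: a failure after day 180 cannot change the day-180 estimate, so the average halves to (ln 2)/n = 0.693/n.

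| Lesions | Days 166-180 | Days 166-194 |
|---|---|---|
| 56 | 1.386/56 = 2.5 points | 0.693/56 = 1.2 points |
| 112 | 1.386/112 = 1.2 points | 0.693/112 = 0.6 points |
| 160 | 1.386/160 = 0.9 points | 0.693/160 = 0.4 points |

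Simulation of the same set-up agrees to within about 0.1 point. For three lesions it gives about 7.2, 3.6 and 2.5 points (days 166-180) and 3.7, 1.9 and 1.4 points (whole window) for 56, 112 and 160 lesions.

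A cruder check ignores timing within the window. With 112 lesions, 22 other losses and 2 affected lesions:
- Censored after the other losses: 1 - 22/112 = 80.4%.
- Censored before them: 1 - 22/110 = 80.0%.
- Counted as failures: 1 - 24/112 = 78.6%.

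The gap is 1.4 to 1.8 points for two lesions, or 0.7 to 0.9 each, inside the range above.

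**The case against.** The sections can be read together. SAP 6.1.9 is a general data-handling rule, and SAP 6.1.5 censors those who are event-free. A lesion scored as lost on angiography has had its event, so the censoring scenario would apply only when neither method is usable. That is a sensible reading and probably the intended one. But SAP 6.3.8 sets its own conditions for censoring and the lesion meets them, so the text does not settle the matter.

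The overlap is narrow, and this stands. It needs a missing or unreadable duplex that the protocol schedules for everyone, an angiogram in the window, restenosis at that lesion, and no clinically driven TLR despite symptoms requiring intervention.

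A reader might infer several stronger things that the documents do not support:
- *That patency rests on duplex alone.* It does not. Freedom from clinically driven TLR is a second component.
- *That the two rules cover the same lesions, so restenosis seen on angiography is generally lost.* A restenosis that led to clinically driven TLR is a failure under SAP 6.3.8.
- *That PSVR 2.5 is the only restenosis figure in the documents.* Inclusion criterion 5b uses restenosis of at least 70% by visual estimate. That is for eligibility; PSVR 2.5 is the only criterion for this endpoint.
- *That scoring retreated lesions as open is an error for assisted and secondary patency.* Counting successful re-intervention is what those measures are for. The choice of image matters for primary patency.

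Finally, Protocol 12.1 refers to separate core laboratory protocols, which are not among the documents reviewed and may say how angiograms are read. They would not remove the conflict inside the SAP.

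**Conclusion.** The point holds as a minor one. For a lesion with an in-window angiogram, no usable duplex and no clinically driven TLR, SAP 6.1.9 and the first censoring scenario of SAP 6.3.8 give different treatment, and the fallback has no restenosis criterion in the SAP or protocol. Followed literally, the censoring scenario drops an observed restenosis, and the resulting error in 6-month primary patency can only be upward.

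Each such lesion is worth about 0.6 to 1.2 points at day 180 with 112 lesions, and about twice that with 56. These figures rest on the assumed visit spread and angiogram timing; the number of affected lesions is unknown and probably small. Patency is secondary and untested, and it plays no part in either primary endpoint or in the study success rule.

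**What to change.** In SAP 6.3.8, narrow the first censoring scenario to lesions with no analyzable duplex, no in-window angiogram of the target lesion and no clinically driven TLR.

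In SAP 6.1.9:
- Apply the fallback when duplex is missing or non-diagnostic.
- For primary patency, use the Angiographic Core Laboratory's reading before any re-intervention, and date a loss at the angiogram.
- Pre-specify a diameter-stenosis cut. Above 50% is one example, mirroring the trial's success cut of at most 50%. That cut was set for the result of the procedure, not for 6-month restenosis, so the final value is the sponsor's choice.
- Report how many lesions were scored by angiography.

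The cost is a few sentences before database lock. No new procedures are needed, since Protocol 12.1 already has the core laboratories assess all angiographic studies. The downside is a possibly slightly lower patency rate and a few lesions scored by a second imaging method.
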